7.4 Reporting Procedures

When participants report an AE or SAE a description of the AE will be recorded in REDCap and brought to the attention of the PI who will then determine if it is study related. Clinicians will make a note during the 8-week sessions, if any adverse effect comes up and report it to the study team who will record the event on the Important Medical Event Form and then notify the PI. Any unanticipated problems involving risk to subjects or others and study-related will be reported to IRB as per the University of Pittsburgh sIRB guidelines. (Refer to the “Adverse Event workflow” sheet for information on how and when to report AEs/SAEs or Unanticipated problems)

7.5 Follow up for Adverse Events

We will follow patients until the adverse event is resolved.

7.6 Safety Monitoring

A formal Independent Monitoring Committee will be set up which will follow the procedures of the NCCIH.

8. INTERVENTION DISCONTINUATION

Circumstance for Withdrawal without Consent:

Withdrawal Procedures: Participants are permitted to withdraw from the study at any time during the intervention or follow-up process. To withdraw from the study, participants should contact the PI at the corresponding site. Participant data prior to withdrawal will be retained in the case of withdrawal from the study.

9. STATISTICAL CONSIDERATIONS

9.1 General Design Issues

OPTIMUM is a multi-site Randomized Controlled Trial/ Pragmatic Clinical Trial (PCT) to treat chronic low back pain (cLBP) in primary medical settings using mindfulness through a telehealth HIPAA-compliant videoconferencing format. The study participants will be randomized at an individual level.

Specific Aims of the study are

Primary Objective, Aim 1: To integrate and test an evidence-based mindfulness clinical pain program, OPTIMUM, for patients with cLBP in the primary care setting.

Primary Hypothesis: Patients in OPTIMUM will have significantly improved pain intensity and interference as measured by the PEG composite score at completion of the program and 6 months (primary end point) and 12-months later, as compared to PCP Usual Care.

Hypothesis 2: Patients in OPTIMUM will have significantly improved psychological function as measured by the PROMIS-29 Mental Health Summary Scale at completion of the program and 6-and 12-months later, as compared to PCP Usual Care.

Hypothesis 3: Patients in OPTIMUM will be less likely to start and more likely to reduce or stop an opioid prescription for cLBP as compared to those in PCP Usual Care.

Secondary Objective, Aim 2: To evaluate use of healthcare resources by patients as documented in the EHR.

Hypothesis: Patients in OPTIMUM will have fewer emergency department visits, fewer hospitalizations, fewer imaging procedures (CT/MRI), and fewer procedures (injections, surgery) than PCP usual care.

Secondary Objective, Aim 3: To evaluate PCP and practice site use of, satisfaction with, and integration of OPTIMUM.

9.2 Sample Size and Randomization

Our target sample size of 450 patients with cLBP \geq 18 years of age will be individually randomized either to an

- 1) 8-week mindfulness clinical pain program (n=225) + PCP Usual Care or
- 2) PCP Usual Care (n=225).

Randomization and Treatment Assignment Procedure

To ensure balance between groups, we will use permuted block randomization with block size of 4 or 6, in a 1:1 ratio, stratified by clinic and sex. Co-I [name] (lead statistician) will generate the randomization sequence using SAS version 9.4, which will be implemented in the database so that the group allocation will be revealed only when each patient consents and is randomized. The randomization schedule will be created prior to enrollment and the study statistician will remain blinded to treatment assignment. We chose to randomize at the patient level rather than at the cluster level (provider or clinic) based on our responses to design choice clarification questions recommended by the NIH Collaboratory: 1) the impact of the pain program in the real-world setting is primarily at the level of the individual patient, as OPTIMUM is delivered to the patient and not the provider, for example, we are not studying implementation of provider treatment guidelines, which could result in contamination if randomized at the patient level 2) randomization at the patient level will not interfere with usual care for the patient with cLBP 3) contamination, if it occurs, will be minor. Contamination cannot be completely eliminated in either cluster or traditional RCT designs and we expect either design has a small risk of staff or patients discussing study details (“comparing notes”) as medical care is delivered in teams and patients go to a variety of clinics depending on appointments with specialists. Additionally, randomization at the patient level allows for efficient use of limited resources (reducing cost and time to completion of the study) while still including a large sample size and maintaining scientific rigor.

9.3 Definition of Populations

All analyses for treatment group comparisons will use the original treatment assignment as randomized for each participant (intention-to-treat). We will also perform a per-protocol analysis for the primary outcome for participants who attended at least 6 out of 8 (75%) of sessions.

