At the *fifth* week's session, walking meditation or mindful movement may be introduced. How to use mindfulness meditation methods to work with pain will be discussed. This will occur at this and the sixth session. Participants will also be taught how to work with pain during formal meditation. They will learn this by a guided meditation during this session, as well as a recording of the body scan that is specific for working with pain.

At the *sixth* week's session, mindfulness in interpersonal relationships and everyday life will be discussed. There will be a review of using mindfulness methods to work with pain, as well as interactive discussion of participants' use of mindfulness to work with pain.

At the *seventh* week's session, using mindful attention to perceive the choices that are available at this moment, and that can affect our pain, health, and well-being will be discussed.

The *eight* week's session will include discussion of the application of mindfulness to everyday situations as well as breaking through habitual tendencies of coping with pain. Integrating what has been learned over the course of the program will be reviewed.

All sessions may include yoga.

Mindfulness instructors have flexibility to review content in a different order so that they can customize their instruction to the participants.

The structure of each session will be approximately 45 minutes (total) of meditation and 45 minutes of discussion. This format was applied successfully during our large clinical trial.⁵

PCP Usual Care Control: PCP Usual Care was chosen as the comparator as it is currently the most commonly used treatment option for patients with cLBP. We will verify patients' attendance at a PCP visit during the study through the EHR as well as the meditation instructor taking attendance. Participants in the PCP usual care control group will be given the option to receive the OPTIMUM mindfulness pain management program at the end of their participation in the study.

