5.4 Adherence Assessment

Assessment and monitoring: Attendance at group sessions will be obtained through the EHR (registered appointment) as patients will need to check in as a telehealth visit and that check-in is logged into the EHR. Unblinded study staff will record attendance. Adherence-promoting strategies include providing guided meditation recordings and instructional materials. Group sessions will stress the importance of home practice and group participation, and discussion will include problem-solving around barriers to the meditation practice and coping with pain.

Treatment fidelity and credibility: The mindfulness instructors will meet weekly during the first 6-months of the UH3 phase of the trial along with [name], [name], and [name] to discuss the delivery of the program in primary care through a telehealth video format, review the structure and format of the sessions, and troubleshoot barriers as they arise. After the first 6-months meetings will be biweekly and starting in Year 2 of the UH3 will be monthly. More frequent or less frequent meetings will be at the discretion of the group. It is critical during this demonstration project to meet regularly to address issues of program delivery and integration into clinic. Additionally, [name] has been trained in the use of the Mindfulness-based Interventions-Teaching Assessment Criteria (MBI-TAC), a standardized system for rating competency of mindfulness instructors and she will be able to provide guidance on evaluating treatment fidelity in a pragmatic setting. Training and monitoring at the three HCS sites will consist of: 1) a combined 3-hour online MGV training led by the respective site PIs and facilitated by [name]; 2) weekly to monthly meetings, as noted above; and 3) facilitator evaluation and group fidelity monitoring, led by [name].

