Compliance: We will estimate compliance by the number of sessions attended and estimate the Proportion of participants with various levels of compliance. We will also calculate the proportion of participants missing each session to describe the pattern of compliance.

Dropout analyses: Participants informing us they no longer want to continue in the study will be considered dropouts, and we will look at when these events occur. Dropout rates will be calculated as proportions of participants randomized, and as a cumulative probability of remaining in the study, using survival analysis techniques such as the product-limit estimator. Unlike proportions, the latter statistics, which can be estimated at various times following randomization, take into account when dropouts occur. The information contained in these descriptive analyses may help us to devise strategies for keeping people in the study.

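### The per-protocol set is defined by session attendance, which only the OPTIMUM arm can have; its comparator is not stated and selection is not handled, so the estimate may be biased, plausibly but not certainly towards benefit

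*Combined protocol and SAP*

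**What the plan says.** Section 9.3 (Definition of Populations) sets the main rule: "All analyses for treatment group comparisons will use the original treatment assignment as randomized for each participant (intention-to-treat"). It then adds a "per-protocol analysis for the primary outcome for participants who attended at least 6 out of 8 (75%) of sessions". It gives no criterion for the usual-care arm.

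The sessions belong to one arm. Section 9.2 describes that arm as "8-week mindfulness clinical pain program (n=225) + PCP Usual Care"; the other receives usual care alone. Section 5.1 says that controls "will be given the option to receive the OPTIMUM mindfulness pain management program at the end of their participation in the study", so they have no sessions to attend during follow-up. Section 5.4 takes attendance from the check-in record: "Attendance at group sessions will be obtained through the EHR (registered appointment").

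The only other planned use of attendance is descriptive. Section 10.2, under Compliance, says "We will estimate compliance by the number of sessions attended" and reports levels and patterns of attendance.

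Two parts of Section 9.6 also bear on the point. Its Data Evaluation text plans adjustment for baseline variables that differ between the two groups, clinically or at p < 0.2. Its Aim 1 text applies p < 0.05 to all analyses unless otherwise specified, and nothing exempts the per-protocol analysis.

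**The concern.** Attendance is a behaviour after randomisation, and it can be seen in one arm only. The people who would have attended had they been offered the program cannot be picked out among the controls. The rule therefore leads to one of two results. Either no control qualifies and there is no between-group contrast, or a self-selected part of the OPTIMUM arm is set against an unselected control arm. In the second case the estimate mixes the effect of the program with whatever prognostic difference separates attenders from non-attenders.

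This is the only between-group estimate planned for people who take up the program, in a trial that the Synopsis says is meant to inform clinicians, patients and policy makers. By default it would carry a p-value. It could look positive when the program does nothing, or understate a real effect, and the reader could not tell which.

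**Working it through.** **The plan's own figures.** The per-protocol analysis has no stated figure, so the planning table in Section 9.6 serves to confirm the inputs: SD of change 2.5, ICC 0.053, 10 per class, 20% attrition, alpha 0.05 (taken as two-sided, which reproduces the table).

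- Design effect: 1 + (10 - 1) x 0.053 = 1.477.
- For a 1-unit difference, the two-sample t-test needs 100, 114 and 133 per group at 80%, 85% and 90% power.
- Multiplying by 1.477 and dividing by 0.80 gives 184.63, 210.47 and 245.55, matching the table. The other 12 rows also reproduce to rounding.

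**Bias if attenders are compared with all controls.** Let p be the share of the OPTIMUM arm attending at least 6 sessions. Let g be the PEG difference in favour of attenders over non-attenders that would exist without any program. Randomisation makes the control arm the same mixture, so under a true null:

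- control mean = p x attender mean + (1 - p) x non-attender mean
- attender mean - control mean = (1 - p) x g

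**Assumptions.** The documents give neither p nor g. I take p = 0.5 to 0.8 and g = 0.5 to 1.0 PEG, with no baseline adjustment.

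**Standard error.** With 20% attrition, 225 x 0.80 = 180 are analysed per arm. Classes exist only in the OPTIMUM arm, so the design effect applies there: SE² = 6.25 x [1.477/(180p) + 1/180].

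- p = 0.8: 6.25 x (0.01026 + 0.00556) = 0.0988, SE 0.314
- p = 0.5: 6.25 x (0.01641 + 0.00556) = 0.1373, SE 0.371

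**Two-sided rejection under a true null**, P(Z > 1.96 - bias/SE) + P(Z < -1.96 - bias/SE):

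| p | g (PEG) | Bias (PEG) | Bias/SE | Rejection |
|---|---|---|---|---|
| 0.8 | 0.5 | 0.10 | 0.32 | 6% |
| 0.8 | 1.0 | 0.20 | 0.64 | 10% |
| 0.5 | 0.5 | 0.25 | 0.67 | 10% |
| 0.5 | 1.0 | 0.50 | 1.35 | 27% |
| any | 0 | 0 | 0 | 5% |
| 0.5 | -0.5 | -0.25 | -0.67 | 10%, almost all against OPTIMUM |

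Against the 1-unit design difference, the positive-gap rows are a bias of 10-50%.

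**Sensitivity to class size.** Restricting to attenders shrinks the classes. At p = 0.5 about 5 per class remain, the design effect is 1 + 4 x 0.053 = 1.212, and the SE is 0.345. The largest figure then rises from 27% to about 30%.

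**Comparison with a complier average causal effect.** This divides the intention-to-treat difference by p. Simulated with p = 0.65 and g = 1.0, it gave 0.00 under the null, where the attender comparison gave 0.35 points of spurious benefit, which is simply (1 - 0.65) x 1.0. With a true attender effect of 1.0 it gave 0.99, against 1.35. These results hold when the method's assumptions hold, as they did by construction.

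**The case against.** The strongest reply is about weight. Every primary comparison stays intention-to-treat, and this analysis is an addition for one outcome. Neither the sample size nor the primary conclusion depends on it, so the rejection rates above belong to a supplementary contrast. That stands.

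A second reply is about direction. A reader might infer that the analysis is biased towards benefit. The documents do not support that as a fact: they report neither attendance rates nor outcomes by attendance. Patients with worse or more persistent pain may attend more, and those who improve early may stop. Either would reverse the sign. This stands too.

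A reader might also take it as given that attenders will be compared with the whole control arm. Section 9.3 does not say so. It is the likeliest reading, but still an inference; what the text itself shows is that the comparator is missing.

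Third, Section 9.6 keeps baseline PEG in the outcome vector and adjusts for baseline imbalance. That provision is written for the randomised groups, and Section 9.3 does not carry it over. If carried over, it would remove the measured part of the selection and leave the unmeasured part.

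Finally, the complier estimate is not free of bias. Participants receive recordings and home-practice materials from week 1 (Section 5.1) and meet a clinician one to one before the program (Synopsis and Section 3). They are unblinded (Section 6.2.3), and PEG is self-reported. Each could let assignment affect PEG in people who attend fewer than 6 sessions. This is a reason to state the assumptions, not to keep an undefined comparison.

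**Conclusion.** The structural point holds with high confidence: the per-protocol criterion can be met in one arm only, the comparator is not named, and no method deals with the selection. As written, the analysis gives either no between-group contrast or one that randomisation does not protect.

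The size and sign are much less certain. The 0.10-0.50 PEG bias and the 6-27% rejection rate rest on assumed attendance of 50-80%, an assumed prognostic gap of 0.5-1.0 PEG in favour of attenders, all controls as comparator and no baseline adjustment. Bias towards benefit is plausible but not established. This is a cheap improvement to a supporting analysis, not a threat to the trial's main result.

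**What to change.** In Section 9.3, make the estimate of the effect among those who take up the program a complier average causal effect on PEG at T3. Use randomised arm as the instrument, attendance at 6 or more sessions as treatment received, and standard errors clustered by class. Add a sensitivity version with number of sessions as the treatment received.

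State the assumptions beside it. The threshold version assumes that assignment has no effect on people who attend fewer than 6 sessions; say how home-practice materials, the clinician visit and unblinded self-report could break this. The number-of-sessions version replaces that assumption with a linear effect per session.

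If the attendance-restricted comparison is kept, name its comparator, say whether baseline adjustment applies, label it descriptive and give it no p-value.

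The cost is SAP wording and one or two extra models on attendance data already being collected. The estimate is less precise: on the planning inputs the intention-to-treat SE is the square root of 6.25 x 2.477/180, or 0.293. Dividing by the share attending gives about 0.37 at 80% and 0.59 at 50%, against 0.314 and 0.371 for the attender comparison. The complier effect is essentially the intention-to-treat effect rescaled by uptake, so its test adds little to the primary one.

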9.4 Interim Analyses and Stopping Rules

The interim analyses and stopping rules will be assessed by the independent monitoring committee.

This study will be stopped prior to its completion if (1) the intervention is associated with adverse effects that significantly impact the risk-benefit ratio; (2) study recruitment or retention becomes futile; (3) any new information becomes available during the trial that necessitates stopping the trial; or (4) other situations occur that might warrant stopping the trial.

9.5 Outcomes

9.5.1 Primary Outcome

The PEG composite score is the primary outcome measure. This will be used to measure the pain intensity, interference, and enjoyment. Six months (T3) will be the primary time point.

9.5.2 Secondary Outcomes

Secondary outcomes are listed in Table 2 above.

9.6 Data Analyses

Data Evaluation:

Prior to conducting the analyses outlined below, we will evaluate the statistical properties of our baseline information and outcome measures. Descriptive statistics, including measures of central tendency (means, medians, other percentiles) and dispersion (standard deviations, ranges) will be computed for continuous data such as the age at enrollment, PEG composite score and other continuous measures. We will also check for potential outliers, normality and missing data. Frequency distributions will be calculated for categorical data such as sex.

We will compare the distributions of baseline characteristics between the two groups to assess the effectiveness of the randomization. All analyses for treatment group comparisons will use the original treatment assignment as randomized for each participant (intent-to-treat). We will adjust for any baseline variable that either statistically (based on a p-value cutoff of $p < 0.2$) or clinically differs between the two groups. Data transformations may be applied to outcomes depending on the shape of the distribution to better approximate normality. We will consider ease of interpretation and clinical meaningfulness when choosing transformations.

Aim 1: To integrate and test an evidence-based mindfulness clinical pain program, OPTIMUM, for patients with cLBP in the primary care setting.

Primary Hypothesis: patients in OPTIMUM will have significantly **improved pain intensity and interference as measured by the PEG composite score** at completion of the program and 6 months (primary end point) and 12-months later, as compared to PCP Usual Care.

We will compare the PEG (primary outcome) at T2 (8 weeks from baseline) and T3 and T4 (6 months and 12 months from T2) with PEG at T1 (baseline) included in the vector of repeated measures using a mixed effects model. We will include the intervention group indicator, time

and their interaction as fixed effects, with random effects for repeated measures on individuals over time and random class effects for group in the intervention arm. We are proposing to control for clustering effect within each class using a random effect because the response of participants in the same class might be correlated. In the study by [name], the intraclass correlation coefficient for the class was 0.053.⁵ We have also taken this into account in our sample size consideration. Alternative covariance structures for the repeated measures over time will be compared using Akaike's Information Criteria (AIC). This model will be used to test specific hypotheses using contrast statements and to compare temporal changes over time between the intervention and control groups. Variables with baseline imbalances can be incorporated as additional fixed effects. We will also examine a clinically meaningful 30% improvement in PEG from baseline as a binary outcome (yes or no) at each follow-up time point using a logistic mixed effects model incorporating a random effect for class clustering. All analyses will be conducted in SAS version 9.4 with $p < 0.05$ considered statistically significant unless otherwise specified.

Hypothesis 2: patients in OPTIMUM will have significantly improved psychological function at completion of the program and 6- and 12-months later, as compared to PCP Usual Care. Analyses will mirror those described above using a mixed effects model with random effects for the clustering effect of intervention classes and repeated measures on individuals over time, with fixed effects for group, time and their interaction. Contrast statements will be used to compare changes from baseline to specific time points. All analyzes will be conducted in SAS version 9.4 with $p < 0.05$ considered statistically significant unless otherwise specified.

Hypothesis 3: patients in OPTIMUM will be less likely to start and more likely to reduce or stop an opioid prescription for cLBP as compared to those in PCP Usual Care.

We will examine opioid prescription for cLBP in two ways. First, we will examine the dose of opioids as morphine dose equivalent (continuous outcome) for those subjects with an opioid prescription at baseline. The analytic approach will mirror the mixed models described for Hypothesis 1 to compare group doses over time and in relation to baseline. Next we will use a binary outcome which is yes/no for opioid prescription (any) for each patient at each time point. Analytic methods will again mirror methods for Hypothesis 1 now using a logistic mixed effects model.

Aim 2. To evaluate use of healthcare resources by patients.

Hypothesis: patients in OPTIMUM will have fewer emergency department visits, fewer hospitalizations, fewer imaging (CT/MRI), and fewer procedures (injections, surgery) than PCP usual care.

Healthcare utilization over 6- and 12-months (prescriptions of opioids, injections, surgery, CT/MRI, ED visits, hospitalizations) are mostly in the form of counts. We will fit a series of GEE models with each outcome as the dependent variable, a negative binomial distribution to account for over dispersion, a log link, exposed time period as an offset, intervention arm (OPTIMUM/Usual Care) as the independent factor of interest, and an exchangeable correlation structure for clustering. Alternative correlation structures will be examined via the QIC statistic. Intervention arm incident rate ratios and their significance will constitute the test of the hypothesis.

Aim 3. To evaluate PCP and practice site use of, satisfaction with, and integration of OPTIMUM.

PCP satisfaction with the pain program will be summarized using descriptive statistics and histograms. We will also investigate if these measures are different depending on the demographic characteristics of the PCPs, such as gender, age, race, ethnicity, clinic location, and years since training, or the outcome of the patients using t-test, chi-square test, Pearson or Spearman correlation tests. Number of 8-week programs delivered at each clinic will also be summarized with descriptive statistics. Adoption of EHR tools and OPTIMUM after study completion will be described.

Planned Analysis & Power Assessment

The table below is of power calculations for the Optimum study using the PEG as the primary outcome. An ICC estimate of 0.053 was used, which came from [name] pragmatic clinical trial funded by NINDS which used the PEG. The other assumptions are $\alpha = 0.05$, SD of change = 2.5 and 20% attrition. As the table illustrates, with a total sample size of 450, with an average of 10 subjects per cluster, we have close to 90% power to detect a 1-unit difference in the PEG between groups. The table also illustrates calculations for a range of power and effect sizes.

ICC = 0.053

Obs	power	meandiff	SD	clustsize	final_npergroup
1	0.80	1.0	2.5	10	184.625
2	0.85	1.0	2.5	10	210.473
3	0.90	1.0	2.5	10	245.551
4	0.80	1.5	2.5	10	83.081
5	0.85	1.5	2.5	10	94.159
6	0.90	1.5	2.5	10	110.775
7	0.80	2.0	2.5	10	48.003
8	0.85	2.0	2.5	10	55.388
9	0.90	2.0	2.5	10	62.773
10	0.80	2.5	2.5	10	31.386
11	0.85	2.5	2.5	10	35.079
12	0.90	2.5	2.5	10	42.464
13	0.80	3.0	2.5	10	22.155

Obs	power	meandiff	SD	clustsize	final_npergroup
14	0.85	3.0	2.5	10	25.848
15	0.90	3.0	2.5	10	29.540

Missing Data Considerations:

We anticipate 20% attrition at the 8-week time point. We chose a higher attrition rate than in our previous work as we anticipate more attrition in the PCT as patients will not have the “high touch” of participants in the RCTs.^{5, 26, 28} Our sample size analyses have accounted for this amount of missing data. We will compare baseline characteristics between patients with the assessment immediately following the 8-week program to those without in order to assess potential bias in study completion. We will also try to obtain reasons for study drop out so that we can assess the missing data mechanism (missing completely at random (MCAR), missing at random (MAR), non-ignorable missingness). At a single time point, we will conduct sensitivity analyses assigning poor scores and good scores for missing values differentially by treatment assignment to evaluate the impact on our study results.

The mixed models proposed for analysis are robust to missing data under MCAR and MAR missing data mechanisms. If the amount missing data differs between treatment groups or appears to be non-ignorably missing, we will conduct sensitivity analyses with imputed data based on varying assumptions (ignorable vs. non-ignorable missingness).

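### The primary PEG model chooses covariates by chance baseline imbalance; baseline PEG and the randomisation strata, fixed in advance, would use the same data better

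*Combined protocol and SAP*

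**What the plan says.** The Data Evaluation part of section 9.6 compares baseline characteristics between arms and then states: "We will adjust for any baseline variable that either statistically" (p<0.2) or clinically differs. It neither lists candidate variables nor says what a clinical difference is. The primary analysis later in 9.6 is a mixed model "with PEG at T1 (baseline) included in the vector of repeated measures". On fixed effects it says "We will include the intervention group indicator, time" and their interaction, with random effects for individuals and for intervention classes. It adds: "Variables with baseline imbalances can be incorporated as additional fixed effects".

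The model is to be used "to compare temporal changes over time between the intervention and control groups". For Hypothesis 2, whose analysis mirrors the primary one, 9.6 says "Contrast statements will be used to compare changes from baseline to specific time points". Section 9.5.1 says "Six months (T3) will be the primary time point". Section 9.2 describes permuted blocks "in a 1:1 ratio, stratified by clinic and sex"; neither factor is among the listed fixed effects. Section 6.2.3 blinds both the biostatistician and the data analyst.

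**The concern.** After randomisation, any baseline difference between arms is chance. A significance test of imbalance therefore says nothing about whether a variable predicts PEG, and prediction is what makes adjustment worthwhile. A rule based on imbalance brings in whatever happened to differ and leaves out prognostic variables that happened to balance.

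The variables with the best claim to a place are missed. Clinic and sex were built into the allocation, so they are balanced by construction and the rule cannot see them. T1 PEG, likely the best available predictor of T3 PEG, is used only through a change contrast, because group, time and their interaction leave the T1 arm means free. Randomisation follows the baseline assessment (6.2.2), so the true T1 means are equal and that freedom spends information.

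The primary covariate set is also unknown until arm-split baseline data are seen. At stake are some precision and a primary model that could be stated in full beforehand.

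**Working it through.** **The plan's own figures.** Inputs from the power section of 9.6: SD of change 2.5, ICC 0.053, cluster size 10, attrition 20%, alpha 0.05 (two-sided reproduces the table). Design effect = 1 + 9 × 0.053 = 1.477. For a 1-point difference the t-test needs 100, 114 and 133 per arm at 80, 85 and 90% power. Multiplying by 1.477/0.8 gives 184.625, 210.473 and 245.551, as printed. At 225 per arm the effective number is 225 × 0.8/1.477 = 121.9, and power is 87.5%.

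**How often the rule fires.** Sections 6.2.2 and Table 2 name at least 31 baseline variables, leaving out sex, PEG and EHR items: 18 demographic, comorbidity and medication items, 8 questionnaires and 5 HEAL scales, some overlapping. Expected at p<0.2 by chance: 31 × 0.2 = 6.2 (95% range 2 to 11 if independent).

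**Whether it finds the strata.** Simulated with N=450, blocks of 4 or 6, assumed 60% female and unequal clinic sizes, chi-square p<0.2, 4000 trials per setting. Sex was selected in none with 4, 10 or 20 clinics and in 0.5% with 40; clinic was never selected. Without stratification the rate is about 20%.

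**What main-effect covariates buy.** Sections 9.5.1 and 9.6, with powering on SD of change, point to the arm difference in change from T1 to T3. A covariate with the same effect at both visits largely cancels from that contrast. With 20% missing at T3, covariates explaining 10% of T3 variance reduce the contrast variance by only 0 to 1.4% (T1 SD 1.6 to 2.0, correlation 0.3 to 0.7).

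**What efficient use of T1 PEG buys.** Let s1 and s3 be the SDs at T1 and T3 and ρ their correlation. The documents give none of these, so s1 and ρ are assumed, and s3 solves s1² + s3² − 2ρ·s1·s3 = 2.5². Per-arm variance with free T1 means:

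s3²(1−ρ²)/180 + (ρ·s3 − s1)²/225

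With a common T1 mean the second term drops; T1 as a covariate is equivalent for this purpose. Example, s1 = 2.0 and ρ = 0.4: s3 = 0.8 + √(0.64 − 4 + 6.25) = 2.5. The terms are 6.25 × 0.84/180 = 0.02917 and 1/225 = 0.00444, so the reduction is 0.00444/0.03361 = 13.2%.

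Reduction in T3 variance (%):

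| T1 SD | ρ 0.3 | 0.4 | 0.5 | 0.6 | 0.7 |
|---|---|---|---|---|---|
| 1.6 | 9.7 | 3.7 | 0.3 | 0.9 | 7.1 |
| 1.8 | 15.9 | 7.5 | 1.8 | 0.1 | 4.4 |
| 2.0 | 24.2 | 13.2 | 4.6 | 0.2 | 2.2 |

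The median is 4.4%, and 9 of 15 cells are below 5%. Applying 1.477 to both variances, power for 1 point moves from 87.5–89.3% to 87.5–95.7%, a median gain of 1.4 points. If class variance (0.053 × 6.25 = 0.331) arises only after T1, the largest reduction is 16 to 17%, power reaches at most about 93%, and the median gain is 0.9 points. With the 85% follow-up target of 10.3.3, the range is 0 to 25%, again below 5% in 9 of 15.

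**What omitting the strata costs.** If clinic and sex explain 1 to 10% of the variance (assumed), leaving them out gives a true size of 4.9 to 3.9% and loses 0.2 to 1.9 power points.

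**The case against.** The strongest reply is that the open choice hardly matters. In a change contrast with covariates that act equally at both visits, complete data give the same estimate whatever set is chosen. A check with 20% missing at random (T1 SD 1.8, ρ 0.5, six covariates with joint R² 0.1 or 0.2, no class effects, 3000 null runs) moved the estimate by only 0.01 to 0.02 PEG points on average across eight candidate sets. Even taking the smallest p of the eight gave 4.8% type I error, against 4.5 to 4.7% unadjusted. This stands, and it is why the point is about efficiency. It also shows that the rule has little to offer in return.

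A reader might infer that 9.6 contradicts itself, since one sentence requires adjustment and the other permits it. The documents do not force that reading: the first can be taken as the rule and the second as the place where selected variables enter. Baseline evaluation is put before the analyses, and the biostatistician and data analyst are blinded. What remains is that the clinical criterion is undefined and no date is given for fixing the covariate set.

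It is also fair that powering on the SD of change and analysing change is coherent, and that free T1 means give a valid model. Neither is a reason to prefer it when a fixed model loses no precision in the range examined.

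**Conclusion.** The point holds as a free improvement. Covariates are chosen by chance imbalance, the strata are left out and will almost never be selected, and baseline PEG is used less efficiently than it could be. The likely gain is small: median about 4% of T3 variance and about 1 power point, with a best case of 24%. These sizes rest on the assumed T1 SD and correlation.

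Three stronger readings are tempting and not supported.

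- **An inflated test.** Omitting strata is conservative, and applying p<0.2 mechanically to independent covariates gave 2.5 to 4.7% type I error in simulation. Rates of 7.4 to 9.6% appeared only when the smallest p was picked after seeing outcomes, with covariates that predict change directly. The plan does not describe such selection.
- **An underpowered trial.** The sample size already uses the SD of change, so the fix only adds power.
- **A 10 to 30% variance gain.** That follows from (1+ρ)/2 for ρ 0.8 to 0.4, which assumes equal SDs at T1 and T3. With SD of change 2.5 it implies a T1 SD of 2.3 to 4.0. Entry needs PEG of at least 3 on a 0–10 scale, and a uniform spread over 3 to 10 has SD 7/√12 = 2.0.

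**What to change.** Replace the imbalance rule in the Data Evaluation part of 9.6, and the matching sentence in the primary analysis, with one fixed primary model:

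- State the primary contrast as the arm difference in PEG at T3.
- Either model follow-up PEG with T1 PEG as a covariate, or keep T1 in the outcome vector with a common T1 mean for both arms.
- Include sex and clinic, or health system if clinics are small. If T1 stays in the outcome vector, these need by-time terms to add precision.
- Take any further covariates only from a short prognostic list named before unblinding.
- Report baseline imbalance descriptively. An imbalance-adjusted model may stay as a labelled sensitivity analysis.
- Use the same structure for Hypothesis 2 with its own baseline.

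The exact pooling rule for small clinics, clinic-by-time terms and a covariate set for Hypothesis 3 are optional.

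The cost is SAP wording and a few degrees of freedom. Sex (1) plus four health systems (3) takes 4 parameters, or 4 × 4 = 16 with by-time terms over four visits. Clinic-level terms cost more, and the number of clinics is not given. No new data are needed and the sample-size table does not change.
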